### 14.2.1 Study Populations and Analysis Methods

- Analysis Population: data will be summarized for all patients who were selected and met the selection criteria.
- Subgroups analysis will be conducted in patients who are naïve for anti-VEGF treatment. If the sample size allows it, analyses will also be conducted in a subgroup of patients who received 6 or less anti-VEGF treatments prior to the first Ozurdex implant injection.
- Additional groups also may be examined, as deemed appropriate such as according to lens status at baseline (phakic vs. pseudophakic) or according to concomitant treatments (concomitant anti-VEGFs vs. Ozurdex only).

Continuous variables will be described by their mean, SD, median, first and third quartiles, extreme values (minimum and maximum) and the number of missing data.

Categorical variables will be described by the total and percentage of each response and the number of missing data.

Two-sided 95% CI of the mean and of percentage may also be calculated when appropriate. Data may also be presented graphically when relevant.

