### **6.3 SUBGROUPS**

The following subgroups will be considered for analysis:

- Treated with Ozurdex in Switzerland vs. Germany
- Patients who are naïve of any anti-VEGF treatment in the study eye prior to the first Ozurdex injection in the study eye: Yes vs. No [DV].
- Number of anti-VEGF treatments in the study eye prior to the first Ozurdex injection in the study eye: 0, 1 to 3, 4 to 6,  $>6$  [DV].
- Lens status of the study eye during the study period: Phakic throughout vs. Pseudophakic throughout vs. Change from Phakic to Pseudophakic [DV].

- At least one concomitant treatment with anti-VEGF and/or corticosteroids in the study eye: Yes vs. No [DV]

Table 6-1 presents subgroups that will apply for each analysis.

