## **13.0 PRIOR AND CONCOMITANT TREATMENTS AND SURGERIES**

Prior medication/surgery is defined as any medication/surgery taken before the date of the first Ozurdex injection in the study eye. Concomitant medication/surgery is defined as any medication/surgery taken on or after the date of the first injection in the study eye.

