## **15.0 ANALYSES OF THE OBJECTIVES OF THE STUDY**

### **15.1 ANALYSIS OF THE PRIMARY OBJECTIVE**

The primary objective '*To assess reinjection interval of Ozurdex implants in patients with DME in real-world in Germany and Switzerland*' will be assessed by the following outcomes:

- Total number of Ozurdex reinjections in the study eye during follow-up, and considering years after the first Ozurdex injection in the study eye (See definition in Table 21-1).
- Re[injection interval defined in months as: (Date of injection (j+1) – Date of injection j) ÷ (365.25÷12), for j=1,...,n where n is the number of reinjections in the study eye. The result will be rounded to 0.1.

The number of Ozurdex reinjections in the study eye per year will be first summarized using descriptive statistics for the following parameters:

- The total number and percentage of Ozurdex reinjections received during follow-up.
- Number and percentage (with 95% CI) of patients with at least one Ozurdex reinjection during Year 1 (See definition in Table 21-1), and number of reinjections per patient during Year 1, for all patients in the analysis population. Note: the first Ozurdex injection will not be considered here, only reinjections will be counted.
- Number and percentage (with 95% CI) of patients with at least one Ozurdex reinjection and number of reinjections per patient during Year k (k=2, 3), for patients having a complete Year k of follow-up (see definition of 'Complete year' in Section 21.2).
- Number and percentage of patients receiving each Ozurdex reinjection (first, second, third, etc) for each year of follow-up (Year k, k=1 to 3) considering patients having the complete year of follow-up.

The Ozurdex reinjection interval in the study eye will be described using descriptive statistics for the following parameters:

- Re[injection interval (months) considering all eligible reinjections recorded in the EDC. The 95% CI of the mean will also be presented.
- Re[injection interval (months) considering each reinjection separately (i.e. first reinjection, second reinjection, etc). 95% CI of the mean will also be presented.

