### Relationship between reinjection interval and drug effectiveness

The potential relationship between Ozurdex reinjection interval and BCVA will be assessed by considering, for each Ozurdex injection  $j$  ( $j \geq 1$ ) in the study eye, the time interval between injection  $j$  and injection  $(j+1)$  and BCVA change from the value prior to injection  $(j+1)$  to 7-12 weeks following injection  $(j+1)$ . All injections of the patient will be considered all together for this analysis.

As a first approach, a figure (scatter plot) defined by Ozurdex reinjection interval (in months) on the horizontal axis and BCVA change (in ETDRS letters) on the vertical axis will be plotted. A linear regression line along with the spearman rank coefficient and p-value will be superimposed on the data of the scatter plot.

As a second approach, the median Ozurdex reinjection interval will be calculated considering all reinjection intervals for a patient. BCVA change (in ETDRS letters) will be then summarized using descriptive statistics by reinjection intervals categorized in two classes according to the median ( $\leq$  median;  $>$  median). The 95% CI of the mean BCVA change will be provided in each class. Based on the observed distribution, other categories than the median may be considered to categorize the reinjection interval.

The same analysis will be performed considering, for each Ozurdex injection  $j$  ( $j \geq 2$ ) in the study eye, the time interval between injection  $j$  and injection  $(j+1)$  and BCVA change from the value prior to the first Ozurdex injection in the study eye (=baseline value) to 7-12 weeks following injection  $(j+1)$ .

A similar analysis will be performed to assess the potential relationship between reinjection interval and CRT in the study eye.

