### Follow-up period

The period starting the day after the day of the first Ozurdex injection in the study eye is the follow-up period (= post-baseline period). End of follow-up occurs at the last study visit or first receipt of concomitant treatment with anti-VEGF and/or corticosteroids, whichever comes first.

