The variable will be derived using information reported in eCRF section '*Prior intravitreal injections/Corticosteroids in Study eye*' (PII/F6 form). The variable will be derived to:

- Yes, if at least one anti-VEGF treatment is reported (= check box ticked)
- No,
  - if the variable '*1.0.1 - Prior to first Ozurdex injection in the study eye for DME, did the patient receive any anti-VEGF or Corticosteroid therapy to treat the study eye?*' is equal to 'No',

- or if the variable '*1.0.1 - Prior to first Ozurdex injection in the study eye for DME, did the patient receive any anti-VEGF or Corticosteroid therapy to treat the study eye?*' is ticked to 'Yes', no anti-VEGF treatments are reported and at least one corticosteroid treatment is reported.
- Missing,
  - if the variable '*1.0.1 - Prior to first Ozurdex injection in the study eye for DME, did the patient receive any anti-VEGF or Corticosteroid therapy to treat the study eye?*' is missing
  - or if the variable '*1.0.1 - Prior to first Ozurdex injection in the study eye for DME, did the patient receive any anti-VEGF or Corticosteroid therapy to treat the study eye?*' is equal to 'Yes' and no treatments have been reported in the table (neither anti-VEGF nor corticosteroids treatments)

At least one corticosteroid therapy in the study eye prior to the first Ozurdex implant injection in the study eye (Yes, No).

This variable will be derived in the same way that the variable '*At least one anti-VEGF treatment prior to the first Ozurdex implant injection in the study eye*' (See definition above).

At least one concomitant anti-VEGF treatment in the study eye (Yes, No)

The variable will be derived using the date of the first Ozurdex injection in the study eye (eCRF section '*Inclusion and Exclusion Criteria*' (IE/F1 form)), the side of the study eye (OS/OD, eCRF section '*Demographics and DME history*' (DM/F2 form)) as well as information reported in eCRF section '*Concomitant Medications (inclusive of intravitreal injections, systemic Steroids, and IOP medications)*' (CM/F18 form). The variable will be derived to:

- Yes, if at least one anti-VEGF treatment is reported with '*1.6.1 - Specify eye*' = {the side of the study eye, 'OU'}
- No,
  - If the variable '*1.1 - Were any ophthalmic concomitant medications taken (including intravitreal injections, systemic steroids, and IOP medications)?*' is equal to 'No'

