- Or, if the variable '*I.1 - Were any ophthalmic concomitant medications taken (including intravitreal injections, systemic steroids, and IOP medications)?*' is equal to 'Yes' and no anti-VEGF treatments are reported
- Or, anti-VEGF treatment(s) are reported however for all anti-VEGF treatments '*I.6.1 - Specify eye*' is equal to the side of the contralateral eye
- Missing,
  - If the variable '*I.1 - Were any Ophthalmic Concomitant Medications taken (including Intravitreal injections, systemic Steroids, and IOP medications)?*' is missing
  - Or, if the variable '*I.1 - Were any Ophthalmic Concomitant Medications taken (including Intravitreal injections, systemic Steroids, and IOP medications)?*' is equal to 'Yes' however no medications have been reported in the form
  - Or, if at least one anti-VEGF treatment is reported with '*I.6.1 - Specify eye*' that is missing and there is no anti-VEGF treatment reported with '*I.6.1 - Specify eye*' = {the side of the study eye, 'OU'}.

At least one concomitant corticosteroid therapy in the study eye (Yes, No)

This variable will be derived in the same way that the variable '*At least one concomitant anti-VEGF treatment in the study eye*' (See definition above).

At least one concomitant anti-VEGF or corticosteroid therapy in the study eye (Yes, No)

The variable will be defined from the 2 derived variables '*At least one concomitant anti-VEGF treatment in the study eye*' and '*At least one concomitant corticosteroid therapy in the study eye*'. It will be derived to:

- Yes, if '*At least one concomitant anti-VEGF treatment in the study eye*' and/or '*At least one concomitant corticosteroid therapy in the study eye*' is equal to 'Yes'.
- No, if '*At least one concomitant anti-VEGF treatment in the study eye*' and '*At least one concomitant corticosteroid therapy in the study eye*' are both equal to 'No'.
- Missing, if '*At least one concomitant anti-VEGF treatment in the study eye*' and/or '*At least one concomitant corticosteroid therapy in the study eye*' is missing and none of them are equal to 'Yes'.

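### The concomitant-treatment subgroup is an ever/never flag per patient, but it splits outcomes counted per interval and per injection, so an unknown share of its Yes group has no concomitant exposure

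*SAP*

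**What the plan says.** **The flag.** SAP 6.3 lists the subgroup "At least one concomitant treatment with anti-VEGF and/or corticosteroids in the study eye: Yes vs. No [DV"]. SAP 21.3.1 sets the anti-VEGF part to "Yes, if at least one anti-VEGF treatment is reported with" the study eye or both eyes as its side, and treats corticosteroids in the same way. For the combined flag, "The variable will be defined from the 2 derived variables": either one being Yes is enough. On timing, SAP 13.0 states: "Concomitant medication/surgery is defined as any medication/surgery taken on or after the date of the first injection in the study eye". Nothing ties a treatment to a particular interval or injection.

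**The outcomes.** SAP 15.1 describes the reinjection interval "considering all eligible reinjections recorded in the EDC", without defining eligible. For the interval-effectiveness analysis, SAP 15.2.1 states: "All injections of the patient will be considered all together for this analysis".

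**End of follow-up.** SAP 21.2 states: "End of follow-up occurs at the last study visit or first receipt of concomitant treatment with anti-VEGF and/or corticosteroids, whichever comes first".

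**The protocol.** Section 14.2.1 offers, as an example of additional groups that may be examined, a split "according to concomitant treatments (concomitant anti-VEGFs vs. Ozurdex only". Corticosteroids are not named. SAP 22.0 lists two changes from the protocol, on the reason for initial injection and on the contralateral eye, and does not mention this one.

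**Where it applies.** SAP 6.3 lists five subgroups. Table 6-1 is broken in the available text and the heading of this column is missing, but its five marks for the primary and first secondary objectives are consistent with the flag being used for both.

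**The concern.** The split is of interest because another intravitreal treatment might postpone the next implant or change BCVA and CRT in the 7-12 week window. A reader will use it to judge whether the results reflect Ozurdex alone.

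The flag cannot answer that. In a Yes patient, an interval completed before the first other treatment is tabulated as concomitant, as is any later interval without one. A patient whose only other treatment came after the last implant contributes nothing but Ozurdex-only intervals. Mixing unexposed with exposed observations pulls a real difference towards zero, and a table showing little difference could be misread as evidence that added treatment does not matter. Because corticosteroids are merged in, a patient who never received a concomitant anti-VEGF can also be a Yes, so this is not the group named in the protocol.

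**Working it through.** The plan states no figure on this point, so there is none to reproduce.

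**1. Two readings of which data count.**

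- *SAP 21.2 governs.* Follow-up stops at the first concomitant treatment, so no interval completed within follow-up contains an earlier one. The unexposed share of Yes intervals is 100%. Yes patients treated before their first reinjection contribute no interval at all. The split then compares pre-treatment intervals of later-treated patients with intervals of never-treated patients.
- *SAP 21.2 does not govern*, and 15.1 takes every recorded reinjection. Exposed and unexposed intervals are then mixed, as follows.

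**2. Arithmetic for one Yes patient.** With m intervals, of which k contain a concomitant treatment, the unexposed share is (m − k)/m. For k = 1:

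| m | unexposed share |
|---|---|
| 1 | 0/1 = 0% |
| 2 | 1/2 = 50% |
| 3 | 2/3 = 67% |
| 5 | 4/5 = 80% |

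Treatment only after the last implant means k = 0 and a share of 100%. Inclusion criterion 1 requires two implants, so m = 1 is possible.

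**3. Simulated range.** From the documents: mean interval 4.7 to 6.7 months and SD 1.5 to 3.0 (SAP 19.0), and at least two implants. Assumed: gamma-distributed intervals, follow-up uniform on 12 to 44 months, and treatments at random times. The frequency of treatment is not in the documents, so a range is shown.

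| concomitant treatments | unexposed share of Yes intervals |
|---|---|
| exactly one per patient | 77-85% |
| 0.5 per year | 67-78% |
| 1 per year | 55-68% |
| 2 per year | 35-52% |
| 4 per year | 15-32% |
| 6 per year | 6-21% |

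Under the first reading in step 1, the Yes patients left with no interval make up 18% to 94% across the same scenarios.

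**4. Dilution.** Let u be the unexposed share, and suppose that unexposed observations in Yes patients behave like those in No patients. Then observed difference = (1 − u) × true difference. At u = 0.85 the table would show 1 − 0.85 = 15% of a true difference; at u = 0.06, 94%; at u = 1, none. For the interval itself this is only approximate, for the reason in step 5.

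**5. Test of the obvious repair.** Suppose an interval is classed as exposed when an anti-VEGF falls anywhere inside it. Longer intervals have more time to contain one. With no true effect (mean 5.5, SD 2.5 months; 0.1 to 0.8 episodes per year, as single injections or courses of three monthly injections):

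| classification | spurious difference in mean interval |
|---|---|
| treatment anywhere in the interval | 0.84 to 1.23 months |
| SAP patient flag | 0.03 to 0.10 months |
| fixed early window after injection j, among intervals still open at its end | about 0.1 month or less |

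The obvious repair is therefore worse than the flag for the primary outcome. The BCVA and CRT changes are not durations, so classifying them by treatment between the two measurements does not carry this bias.

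**The case against.** The strongest reply is that this is a descriptive study. Protocol 6 says that no hypothesis underlies the objectives, and Protocol 8.2 rules out causal conclusions. The label openly says at least one treatment. SAP 13.1 already tabulates the time from each reinjection to the first anti-VEGF and corticosteroid. The patient flag is also nearly free of length bias. All of this is correct. It limits the consequence, but it does not make the subgroup table interpretable as a comparison of treatment with and without added therapy.

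Three stronger readings are tempting and are not supported.

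- *That most Yes intervals are Ozurdex-only.* This needs a frequency of concomitant treatment, and none is given. It holds for sparse use and fails for repeated use. Protocol 5.1 itself describes anti-VEGF treatment as needing monthly injections over an extended period.
- *That a patient-level flag breaches the protocol.* Protocol 14.2.1 gives an optional example and speaks of groups; it defines no interval-level contrast. The documented difference is the added corticosteroids.
- *That the dilution can be judged against the 0.2-0.5 month half-width in SAP 19.0.* That figure is the precision of a single mean in 150 patients, not of a subgroup difference.

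**Conclusion.** The point holds in a limited form. The documents establish an ever/never patient flag applied to per-interval and per-injection outcomes, subject to the unreadable column in Table 6-1. They also establish an unlisted widening from anti-VEGF to anti-VEGF or corticosteroids, and an end-of-follow-up rule not reconciled with the reinjections analysed in SAP 15.1.

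The unexposed share of the Yes group is 100% if SAP 21.2 governs. Otherwise it is unknown, anywhere from 0% to 100% in principle and about 6% to 85% in the simulated scenarios, which rest on assumed rates and random timing. Dilution towards no difference is the expected effect, but confounding by indication could move the comparison either way. The overall mean interval does not depend on this flag. The change is inexpensive and worth making before analysis.

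**What to change.** 1. Reconcile SAP 21.2 with 15.1: define eligible reinjections and state whether data after the first concomitant treatment are analysed. If they are not, drop this subgroup from 15.1 and 15.2.1, or label it as patients who later received other treatment.
2. If they are analysed, in SAP 15.2.1 classify each BCVA or CRT change by whether a study-eye anti-VEGF was given between the pre-injection value and the last value used in the window. Show non-Ozurdex intravitreal corticosteroids as a separate class.
3. For the interval in SAP 15.1, do not class by treatment anywhere inside the interval. Choose one of: exposure in a fixed early window after injection j, among intervals still open at its end; anti-VEGF as a time-varying factor; or the existing flag relabelled as ever received.
4. List the change of definition in SAP 22.0.

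The cost is SAP wording and one or two derived variables, with no new patients or data. Protocol 10.4.3 records other intravitreal injections at each visit, and SAP 13.1 already uses their timing. Treatment dates with a missing day are set to the first of the month (SAP 21.4), which can place a treatment on the wrong side of an injection; such cases should be counted.

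The exposed classes will be smaller, and one patient can contribute to both. The early-window analysis omits intervals shorter than the window. The comparison remains descriptive and open to confounding by indication.

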**Table 6-1 Planned Subgroup Analyses**

Analysis	Subgroups				
Demographics and other baseline characteristics (Section 10.0)	X	Treated with Ozurdex in Switzerland vs. Germany	Patient naïve to anti-VEGF in the study eye prior to the 1 st Ozurdex injection in the study eye: Yes vs. No	Number of anti-VEGF treatments in the study eye prior to baseline: 0, 1 to 3, 4-6, >6	Lens status of the study eye during the study period: Phakic throughout vs. Pseudophakic throughout vs. Change from Phakic to Pseudophakic
Diabetes and DME status (Section 11.0)	X				X
Clinical examination in the study eye (Section 12.0)	X				
Prior and concomitant treatments and surgeries (Section 13.0)	X				
Primary objective (Section 15.1)	X	X	X	X	X
First secondary objective (Section 15.2.1)	X	X	X	X	X
Second secondary objective (Section 15.2.2)	X	X	X		X
Third secondary objective (Section 15.2.3)					
Fourth secondary objective (Section 15.2.4)	X				

The planned subgroup analysis specified in Table 6-1 above may not be performed if the number of patients in the subgroup is too small.

## **7.0 BIAS AND LIMITATIONS**

Selection bias is a potential limitation of the study, for both sites and patients. Sites will be selected from hospital-based experienced medical retina centers treating DME patients, as these centers will be experienced in intravitreal Ozurdex injections. Because the participating sites comprise a population of volunteers, non-response bias is possible.

In order to limit bias in the selection of patients, sites will attempt to consecutively select all patients who meet the selection criteria, regardless of demography or other considerations, based on the date of first Ozurdex implant injection. All patients meeting the selection criteria, regardless of their selection for the study, will be identifiable in a screening log collecting minimum non-identifying patient information (see Section 6.1). Characteristics of selected and non-selected patients will be compared to assess patient selection bias and reason for not being selected will be described (patient did not meet selection criteria, lack of time, quotes were met, etc.).

Information bias is a distortion in the estimate of association between risk factor and disease due to systematic measurement error or misclassification of patients on one or more variables, either risk factor or disease status. As the study is retrospective, it relies on data that have already been collected for another purpose (i.e. patient care). As a result, not all data to be collected in this study may be recorded in the medical charts, leading to a potential bias due to missing data. Moreover, as the study is anonymous, no queries will be issued to the sites in case of missing or incoherent data. Finally, as this is a multicenter study, the methods used to estimate the variables collected during the chart review process may be heterogeneous across sites. This has the potential to introduce systematic bias into the results.

Information bias is minimized by the use of EDC technology. In addition, to minimize the burden on investigators and sites, the EDC will maximize the quality and relevance of the data using automated online controls. To complement these automated online controls, principal investigators will be requested to review all entered data submitted in the EDC.

Confounding bias may result from selective prescribing of a particular treatment to more severely affected patients. As a result of higher background risk, reported event rates may be higher and give the appearance of an elevated risk related to the use of treatment. The collection of relevant medical information prior to first Ozurdex implant injection will help to identify the presence of elevated background risk of safety events, so that safety events can be compared through subgroup analysis to what was observed in available literature to determine whether the elevated risk is likely to be related to background risk (e.g. previous occurrence of glaucoma, previous cataract, previous anti-VEGF treatment) or use of Ozurdex.

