In the MEADs trials, the most commonly reported AEs following treatment with Ozurdex are those frequently observed with ophthalmic steroid treatment or intravitreal injections: cataract formation, elevated intra-ocular pressure (IOP), and conjunctival or vitreal hemorrhage. In these trials, cataract-related AEs were observed in 67.9% of patients with a phakic eye at baseline compared to 20.4% of patients in the sham group. The incidence of cataract-related AEs increased after the first year after Ozurdex injection. Approximately one-third of patients with Ozurdex implant had a clinically significant increase in IOP requiring treatment during the study. Vitreous hemorrhage considered possibly related to treatment was reported in 3.5% of patients with Ozurdex implant compared to 0.0% in the sham group. Less frequently reported but more serious adverse drug reactions include endophthalmitis, necrotizing retinitis, retinal detachment and retinal tear. With the exception of headache and migraine, no systemic adverse drug reactions were identified with the use of Ozurdex. Finally, several adverse drug reactions, such as conjunctival hemorrhage, visual acuity reduced, vitreous detachment, vitreous floaters, vitreous opacities, eye pain, photopsia, conjunctival edema, conjunctival hyperemia, endophthalmitis, retinal detachment, retinal tear, hypotony of the eye, anterior chamber inflammation, anterior chamber cells/flare, abnormal sensation in eye, scleral hyperemia, device dislocation, and complication of device insertion, have been identified in Ozurdex SmPC as related to the intravitreal injection procedure, i.e. the frequency of these AEs is proportional to the number of treatments given.

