### **7.3.3 Confounding Bias**

Confounding bias may result from selective prescribing of a particular treatment to more severely affected patients. As a result of a higher background risk, reported event rate may be higher and give the appearance of an elevated risk related to the use of the treatment. The collection of relevant medical information prior to first Ozurdex implant injection will help to identify the presence of elevated background risk of safety events, so that incidence of safety events can be compared through subgroup analysis to what was observed in available literature to determine whether the elevated risk is likely to be related to background risk or use of Ozurdex (e.g. previous occurrence of glaucoma, previous cataract, previous anti-VEGF treatment).

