### 15.2.4 Fourth Secondary Objective

The secondary objective '*To present those AESIs that may be potentially related to Ozurdex reinjection*' will be assessed by the presence of the following AESIs:

- Cataract or lens opacities
- Glaucoma
- Hypotony
- Implant dislocation
- Infection vs. Non-infection related ocular inflammation
- Intraocular hypertension
- Mechanical failure of device and implant misplacement
- Ocular bleeding or hemorrhage
- Retinal detachment (tear or hole)
- Significant vitreous loss
- Vitreous detachment

These AESIs will be identified from eCRF section '*Adverse events*' (AE/F20 form) in which they are pre-listed.

All AESIs that began on or after the date of the first Ozurdex injection in the study eye will be considered for analysis. The analysis will be performed:

- considering all AESIs, AESIs that occur in the study eye, and AESIs that occur in the contralateral eye.
- cumulatively considering all AESIs and broken down by the number of injections, i.e. considering AESIs that occur after the first Ozurdex injection at baseline, AESIs that occur after the first Ozurdex reinjection, AESIs that occur after the second Ozurdex reinjection, etc. AESIs that occur on the same day of an Ozurdex injection will be considered as occurring after the injection.

AESIs will be summarized using descriptive statistics for the following parameters:

- Number and percentage (with 95% CI) of patients who experienced at least one AESI.

[REDACTED]

[REDACTED]

[REDACTED]

[REDACTED]

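### The background-risk subgroup comparison promised for safety is not specified for AESIs in the visible plan, and the visible denominator for cataract does not match the phakic-eye rate the protocol quotes

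*SAP*

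**What the plan says.** Protocol 7.3.3 and SAP 7.0 recognise that patients selected for treatment may carry a higher background risk of safety events. Their answer is to collect baseline history "so that safety events can be compared through subgroup analysis to what was observed in available literature". The SAP's examples of background risk are "previous occurrence of glaucoma, previous cataract, previous anti-VEGF treatment"; the protocol gives the same three.

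SAP 6.3 opens with "The following subgroups will be considered for analysis" and lists five groupings: country, anti-VEGF naive or not, number of prior anti-VEGF treatments, concomitant anti-VEGF or corticosteroid treatment, and "Lens status of the study eye during the study period: Phakic throughout vs. Pseudophakic throughout vs. Change from Phakic to Pseudophakic". In Table 6-1 the row beginning "Fourth secondary objective (Section 15.2.4" carries one mark.

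SAP 15.2.4 lists 11 AESIs, with cataract or lens opacities first. It splits them by eye and by number of injections. The one summary statistic left visible is "Number and percentage (with 95% CI) of patients who experienced at least one AESI". Under SAP 6.2, analyses use the whole Analysis Population unless something else is stated.

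Protocol 5.1 supplies the external cataract figure: "cataract-related AEs were observed in 67.9% of patients with a phakic eye at baseline compared to 20.4% of patients in the sham group". The same section says that the approved indication includes pseudophakic patients.

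**The concern.** There are two linked gaps.

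First, the only remedy offered for confounding of the safety results is a subgroup comparison, and the sections that define and assign subgroups do not contain it. SAP 22.0, which lists departures from the protocol, does not withdraw it. The SAP therefore states an intention without specifying an analysis.

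Second, an eye with no natural lens cannot develop a new cataract. If such eyes stay in the denominator, the cataract percentage falls as their share rises, whatever the risk in eyes that can have the event. Set beside a rate for phakic eyes, the result could look reassuring for a reason unrelated to the drug. The same applies, to a smaller and unknown degree, to a pooled percentage with at least one AESI that counts cataract.

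**Working it through.** **Own figures of the plan.** The plan states no expected AESI rate or safety precision, so there is no safety figure to reproduce. Its precision for the primary objective, 1.96 × SD / √150, gives 0.24 to 0.48 months for SD 1.5 to 3.0. That matches the stated 0.2 to 0.5, but has no bearing on AESIs.

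**Step 1: promise against specification.**

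| Factor named in SAP 7.0 | Subgroup in SAP 6.3? | Marked for AESIs in Table 6-1? |
|---|---|---|
| Prior glaucoma | No | Not possible |
| Prior cataract | No (lens grouping is by status during the study) | Not possible |
| Prior anti-VEGF | Yes, two groupings | Apparently not |

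The header of Table 6-1 is broken in the extracted text. The primary-objective row has five marks, matching the five groupings of SAP 6.3. The single mark in the AESI row stands first, and country is the first grouping. That reading is an inference. Whichever column it is, only one of the five groupings is marked, and none of the five is glaucoma or cataract history.

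**Step 2: cataract denominator.** Inputs: risk in phakic eyes 67.9% (protocol 5.1); risk in pseudophakic eyes zero; N = 150 (SAP 19.0); exact Clopper-Pearson intervals (SAP 21.1). The documents do not give the pseudophakic share at baseline; 30% to 70% is assumed.

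Apparent percentage = 0.679 × (1 − pseudophakic share):

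- 30% pseudophakic: 0.679 × 0.7 = 47.5%
- 50% pseudophakic: 0.679 × 0.5 = 34.0%
- 70% pseudophakic: 0.679 × 0.3 = 20.4%

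In whole patients out of 150 (rounding moves the percentages slightly):

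| Pseudophakic share | Phakic eyes | Cases | All patients, % (95% CI) | Phakic at baseline, % (95% CI) |
|---|---|---|---|---|
| 30% | 105 | 71 | 47.3 (39.1–55.6) | 67.6 (57.8–76.4) |
| 50% | 75 | 51 | 34.0 (26.5–42.2) | 68.0 (56.2–78.3) |
| 70% | 45 | 31 | 20.7 (14.5–28.0) | 68.9 (53.4–81.8) |

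With eyes phakic at baseline as denominator, the estimate stays near 68% and only its interval widens.

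**Step 3: an AESI that needs no natural lens.** Protocol 5.1 quotes vitreous hemorrhage at 3.5%, with no restriction to phakic eyes. That is about 5/150 = 3.3% (1.1–7.6) whatever the lens mix.

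**Step 4: what the strata could show.** Protocol 5.1 puts pressure rises needing treatment at about one third. At that rate, 50 anti-VEGF-naive patients give 17/50 = 34% (21–49). The prevalence of prior glaucoma is not given. At an assumed 5%, 10% or 20%, the stratum gives 3/8 (9–76), 5/15 (12–62) or 10/30 (17–53). The anti-VEGF split is informative; the glaucoma split is imprecise.

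**The case against.** Much can be said for the plan, and several stronger readings should be resisted.

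- **A reader might infer that no AESI percentage can be compared with the literature.** The documents do not support that. The lens argument touches cataract and pooled figures that include it. Hemorrhage, hypotony, detachment, inflammation, pressure events and implant problems do not need a natural lens.
- **A reader might infer that no background-risk split exists anywhere.** Protocol 14.2.1 commits in general to an anti-VEGF-naive subgroup and names baseline lens status as a group that may be examined. Neither is tied to AESIs and the second is optional, so this weakens the point without removing it.
- **The cataract-specific text may be hidden.** Parts of protocol 14.2.2.3.4 and SAP 15.2.4 are redacted, and a phakic restriction could stand there. The denominator point therefore concerns only the visible text. The redactions do not touch the list in SAP 6.3.
- **A reader might infer that pre-existing glaucoma or ocular hypertension inflates those AESI rates.** SAP 15.2.4 counts only events beginning on or after the first injection. Eyes already affected may be unable to acquire the condition anew, which lowers the rate; higher background risk may raise it. The net direction is unknown.
- **A phakic denominator alone does not make the rates comparable.** The 67.9% comes from 3-year trials, and protocol 5.1 says cataract events increased after the first year. This study guarantees 12 months, and SAP 21.2 closes the follow-up period at the first concomitant anti-VEGF or corticosteroid treatment. This stands, and the fix allows for it.
- **Some of it can be recovered afterwards.** SAP 12.1 tabulates baseline lens status, so a study-eye rate could be approximated if study-eye cataract counts are reported. Prespecifying it is safer.
- **The aim is descriptive.** The objective is to present AESIs, causal conclusions are disclaimed, and small subgroups may be dropped. This limits the weight of the point, but SAP 7.0 still describes the comparison as a way to tell background risk from drug effect.

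**Conclusion.** The concern holds in a limited form. The visible plan does not deliver the background-risk comparison that SAP 7.0 and protocol 7.3.3 describe. Prior glaucoma and prior cataract have no subgroup at all, and prior anti-VEGF has one that is apparently not applied to AESIs. On the visible text, a cataract percentage would also have a different denominator from the rate quoted beside it.

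The possible size is large: 67.9% in eyes at risk could appear as anything from 47.5% to 20.4%. This is an illustration. It assumes that the trial rate applies here, that pseudophakic eyes have no risk, and that 30% to 70% of study eyes are pseudophakic. The low end coincides with the quoted sham rate only because a 70% share was assumed. A reader might infer that the study will make the implant look like sham, but nothing in the documents predicts that share.

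This is worth correcting before analysis. It concerns a secondary, descriptive objective and does not affect the reinjection-interval results.

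**What to change.** In SAP 15.2.4 and Table 6-1:

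1. Report cataract or lens opacities in the study eye with study eyes phakic at baseline (SAP 12.1) as the denominator. Do not use the lens grouping of SAP 6.3 for this. It is defined by status during the study, and a change to pseudophakic can itself follow from cataract.
2. Report glaucoma and intraocular hypertension AESIs descriptively by whether the study eye had glaucoma or ocular hypertension at baseline (SAP 10.2), with no assumed direction of bias.
3. Mark the anti-VEGF-naive column for the fourth secondary objective.

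In SAP 7.0, limit comparisons with the literature on these factors to these strata, and note that follow-up here differs from the quoted 3-year trials. If redacted text already sets any of these rules, a cross-reference is enough.

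The cost is SAP wording and extra table columns; no new data are needed, since baseline lens status, glaucoma and ocular hypertension history and prior anti-VEGF use are already collected. The price is smaller denominators and wider intervals, most of all in the glaucoma stratum, which may be too small to say much.
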